treatments available. Diabetic Retinopathy is another very prevalent disease. In the U.S., diabetes affects over 18.2 million people. Retinopathy is the most common microvascular complication of diabetes, resulting in blindness for over 10,000 people with diabetes per year. Visual loss can be due to macular edema, macular ischemia, or neovascular complications. The loss of vision due to DR has an enormous impact on the quality of patients' daily lives, and also results in a significant reduction of productivity, imposing a significant socioeconomic burden on our society and on the millions of people who suffer from such disease. Head mounted displays represent a technology that has the potential to increase visual function in patients with low vision. However, current research on stereoscopic and monocular wearable visual enhancement devices has been conducted on individuals with good vision, and using display patterns which were not developed for low-vision applications. As a result, little is known about the effectiveness of these displays on improving visual function and mobility, and reducing asthenopia in visually impaired individuals.

Head-mounted visual enhancement device design:

Evergaze Technology LLC, has designed a head mounted electronic visual enhancement device that is compact and similar to glasses. It will be powered by a battery pack connected to the device. The electronic display will be affixed over only one of the user's eyes. The vision through the unobstructed eye will aid with the subject's balance and spatial orientation. The concept of providing each eye with a different image is not novel. It has been demonstrated to be tolerated successfully in patients with different refractive correction for each eye (monovision), and also in patients that have been implanted with a miniature telescope in one eye.

The prototype display and camera will be connected to a battery pack/control box that will allow the user to quickly select one of 3 modes. Each mode will represent a combination of parameters (inverted black/white magnification) designed to optimize the image for different activities (e.g. reading, walking, computer use).

Figure 1. 3D printout of a prototype design for the visual enhancement device.

Concise Summary of Project:

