b. Question 6: Have a simple test of near visual-motor skills (i.e. a board with small cut-out shapes that the subjects need to put in the correct place) and measure the time it takes them to complete it.

c. Question 7: Have a portable 3 to 5 shelf storage shelf with 20 random items. Ask the patient to find one specific item. Repeat 3 times and record the time it takes the patient for each attempt.

d. Question 11: Show the patient a 15-20 second video (without the audio track) showing a conversation between 2 individuals. Following the video, subjects will be queried about the facial expressions of the actors during the conversation.

4) Having the patient fill out a questionnaire based on the tests administered. Subjects are not excluded based on gender, age, or race. In total, there is a plan to have 1 visit for this project. It should be noted the collection of above mentioned clinical data points will solely be used for the purpose of this research study.

Study Procedures:

It is expected that approximately 20 Aston clinic patients will be enrolled in this trial. No bias or negative consequence will occur to anyone that does not wish to consider this project. After obtaining informed consent, the following procedures will be performed as an aspect of this study:

- Document patient demographics including age, sex, race, and ethnicity
- Review and document of medical and ophthalmic history
- Review and document Ophthalmic diagnosis (Retinal Degeneration or Diabetic Retinopathy) and onset time (in years and months if possible)
- Review and document concomitant use of systemic and ophthalmic therapies including administration of all laser and anti-VEGF therapies
- ETDRS Best Corrected Distance Visual Acuity will be performed
- Best Corrected Near Visual Acuity will be performed using a near card reader
- Wearing refraction (Glasses) will be measured and documented in source forms

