- National Eye Institute Visual Function exams will be administered to each subject as outlined in previous section with and without the head mounted visual assessment device. During the testing portion of the head mounted visual assessment device, head and eye movements will be video recorded by one of the sponsor/manufacturer's agents for this research project.. This will allow the team to assess what kinds of adjustments the subjects are making to optimize their view. Patients will be given a 20-minute break between testing with and without the head mounted visual assessment device.
- Administration and completion of patient questionnaire on their experience with the use of NEI Visual Function exams
- A second study visit identical to this one may be repeated after a period of self-training at home with the device.

Inclusion Criteria:

1. Patient of any sex, race, or ethnicity who are 18 years of age or older. Spanish speaking patients will be encouraged to participate, Spanish forms will be available to review and execute.
2. Patient willing to review, understand, and sign written Informed Consent. Parents or legal guardians will consent on behalf of minors.
3. Written authorization for use or release of health and research study information.
4. Patient who volunteers is suffering from a posterior segment ophthalmic disorder including Retinal Degeneration and/or Diabetic Retinopathy and visual acuity from 20/60 to 20/400 in the better Seeing Eye.

Exclusion Criteria:

1. Subjects will be excluded if they are less than 18 years of age.
2. Subjects will not be considered for this research study if they will not review and execute the informed consent form.
3. During the screening process, subjects will be excluded from further consideration if they are identified with having a potential ophthalmic diagnosis other than Retinal Degeneration or diabetic macular edema that could be negatively affecting the visual testing.
4. ETDRS Visual Acuity better than 20/60 or worse than 20/400
5. During screening, subjects will be disqualified from further assessment if it is determined that their refractive error is outside of the -5.00D to +5.00D corrective range.

Sources of Research Material:

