PI will apprise fellow ophthalmology faculty members in the department regarding the nature of the study through written communication. A referral letter informing the ophthalmology faculty practice at UTSW Medical Center at Dallas will be made available to review. The PI will provide referring ophthalmologists at UTSW Medical Center at Dallas copies of IRB approved forms, including the informed consent. This form will be given by the referring clinician to interested patients during their visit to the clinic.

For patients that are recruited from the PI's clinic, the PI or the clinical coordinator will describe the study in detail and allow the patient time in order to make an informed decision. Consent is only given if the subject completely understands the IC and withdrawal provisions, and agrees to take part in the study. Consent form is signed by the patient who is seeking to join the study and by the principal, sub-investigator, or clinical research coordinator. An executed copy is given to the patient; another is placed in the patient medical chart. The original IC is placed in the regulatory binder along with other important study documents. The regulatory binder is kept in a secure area in the research coordinator office. During the actual clinic visits, each procedure is explained to the subject.

For interested patients that are referred from the faculty clinics at Aston, the coordinator will speak with the prospective patient after treating physician has spoken to the patient about the study and given them the appropriate literature to review. The clinical coordinator will describe the study in detail and allow time for the patient to make an informed decision only after the interested, prospective subject initiates contact with the coordinator regarding the study.

Potential Risks:

There are no known risks associated with the use of the head-mounted visual enhancement device, a similar device has been fabricated previously as a consumer test product for watching movies displayed as High Definition Cinema. The exception of possible temporary disorientation, dizziness, or visual blur due to the monocular aspect of the device exists. The patient will be sitting during the entire

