test, which will last **about 2 hours**. The tester will be constantly supervising the patient during the exam. Another area where there may be an opportunity for potential risk is in protecting patient privacy throughout the course of the study and following the conclusion of the project. A detailed plan is provided in “Procedures to Maintain Confidentiality”.

Subject Safety and Data Monitoring:

Careful oversight of patient safety and wellbeing will be undertaken by the Principal Investigator and Sub-Investigator on this study. In the event of an adverse event during the visits as required by the study protocol, treatment will be provided by the researcher on this study and the affected patient will be stabilized before exited from the study.

Special Precautions:

Procedures to protect against the potential risk of a breach of confidentiality are described in the following section. Any additional physical or psychological risk to patients as a result of this prospective study is not foreseeable as the collection method utilized is typically used in the clinic for standard of care management. Subjects are informed verbally and in the consent form of the following: contact information and the phone number for investigator in case of an adverse event that occurs after the study is initiated. Moreover, the PI will monitor the study for quality assurance purposes.

Procedures to Maintain Confidentiality:

All subject data will remain confidential and access will be restricted to authorized study personnel only, including the principal investigator, sub-investigator, and the study research study. All study information and data will be secured in a locked area and accessible only to study investigators. Patient identifying information will be removed as the pertinent data is transferred to a data collection sheet so that there

is no link to specific identifiers. All electronic study data will be password protected. Data will be presented in aggregate form to the sponsor without specific identifiers.

The Investigator(s) / Institution(s) will permit trial-related monitoring, audits, IRB review and regulatory inspection(s) by providing direct access to source data / documents. Should the clinical site be contacted for an audit by an IRB or regulatory authority, study sponsor should be contacted and notified in writing within 24 hours.

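### No procedure asks about the disorientation, dizziness and blur the protocol expects from the device, so they are likely to be under-counted and cannot be compared with and without it.

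*Combined protocol and SAP*

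**What the plan says.** - **Potential Risks** names the expected physical effects: "The exception of possible temporary disorientation, dizziness, or visual blur due to the monocular aspect of the device exists". It adds that the subject stays seated and is supervised throughout by the tester.
- **Background** says of head-mounted displays that "little is known about the effectiveness of these displays on improving visual function and mobility, and reducing asthenopia in visually impaired individuals". Eye strain thus appears as an open question about benefit, not as a listed risk.
- **Study Procedures** lists demographics, history, therapies, acuity, refraction, the four function tests with and without the device, and video of head and eye movements. Its one subjective instrument is "Administration and completion of patient questionnaire on their experience with the use of NEI Visual Function exams". The Concise Summary of Project describes the same item as "Having the patient fill out a questionnaire based on the tests administered".
- **Study Procedures** also says: "Patients will be given a 20-minute break between testing with and without the head mounted visual assessment device". The order of the two conditions is not stated. An optional second visit may follow self-training at home.
- **Sources of Research Material** requires adverse events to be documented and the notes to be reviewed by the investigator. It does not say how or when events are elicited, or under which condition.
- **Special Precautions** says: "Any additional physical or psychological risk to patients as a result of this prospective study is not foreseeable". The reason given is that the collection method is one used in routine clinic care.
- **Statistical Analysis Plan** specifies paired t-tests on vision and recognition. It has no tolerability outcome.

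**The concern.** The protocol predicts specific symptoms and then schedules nothing that asks about them. Dizziness, disorientation and blur are mainly felt rather than seen, and a seated subject may show no outward sign. Two things are at stake.

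1. **Counting.** A report of few or no events could mean that the device was well tolerated, or that nobody asked. The planned data cannot separate the two.
2. **Comparison.** These patients have low vision and may have such complaints without the device. With no baseline and no record by condition, the rate with the device has nothing to be set against, although each subject is tested both ways.

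The study is meant to inform the requirements for an assistive device, so tolerability belongs among the things it should be able to describe.

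**Working it through.** **Step 1. Look for a symptom question.** Each possible source was read in turn.

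| Source | Asks about the named symptoms? |
|---|---|
| History, therapies, refraction | No |
| Acuity | No; listed once, no repeat after device wear stated |
| Four function tests | No; timings or answers about the task |
| Video of head and eye movements | No; made with the device only, to see how subjects adjust their view |
| VFQ-25 items 5, 6, 7, 11 | No; difficulty with reading, near work, shelf search, seeing reactions |
| Patient questionnaire | Form not reproduced; described as concerning the tests, not stated to be given per condition |
| Adverse event record | Elicitation, timing and condition not specified |
| Statistical Analysis Plan | No safety or tolerability analysis |

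**Step 2. Illustrate the under-count.** The documents give no symptom rate and no capture rate, so both are assumed and varied. Let *r* be the true proportion of subjects with a symptom and *s* the share recorded without asking. The sample sizes are the plan's: 8-10 in the pilot, about 20 in full.

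Chance of recording at least one case = 1 − (1 − *rs*)^n

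| n | r | s = 1 | s = 0.5 | s = 0.25 |
|---|---|---|---|---|
| 8 | 5% | 34% | 18% | 10% |
| 8 | 10% | 57% | 34% | 18% |
| 8 | 20% | 83% | 57% | 34% |
| 10 | 5% | 40% | 22% | 12% |
| 10 | 10% | 65% | 40% | 22% |
| 10 | 20% | 89% | 65% | 40% |
| 20 | 5% | 64% | 40% | 22% |
| 20 | 10% | 88% | 64% | 40% |
| 20 | 20% | 99% | 88% | 64% |

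Worked example, *r* = 20% and *s* = 0.5, so *rs* = 0.10. The chance of an empty record is 0.9^20 = 12% at 20 subjects, 0.9^10 = 35% at 10 and 0.9^8 = 43% at 8. With full capture the figures are 0.8^20 = 1%, 0.8^10 = 11% and 0.8^8 = 17%. Expected recorded cases at 20 subjects are 20 × 0.20 × 0.5 = 2, against 20 × 0.20 = 4 true cases.

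**Step 3. What asking would and would not buy.**

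- With full capture and no cases, the one-sided 95% upper limit, 1 − 0.05^(1/n), is 31% at n = 8, 26% at n = 10 and 14% at n = 20.
- An exact two-sided McNemar test needs at least six discordant subjects, all worse with the device: 2 × 0.5^6 = 0.031, whereas five give 2 × 0.5^5 = 0.0625.
- At n = 20, assume 30% of subjects have a symptom only with the device and 5% only without. Power is then 32%, and it falls to about 5% if both proportions are halved by under-recording. With 50% against 5% and full capture it is 79%.

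The paired symptom data would therefore support description with confidence intervals better than a formal test.

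**The case against.** The strongest reply is that safety capture is unspecified rather than absent. The tester watches the subject throughout, both investigators oversee safety, and adverse event notes are reviewed. Nothing says that events are recorded only when volunteered, and the questionnaire on the subject's experience might include discomfort. The primary objective is functional benefit, and its analysis does not depend on symptom data. All of this stands, and it limits the point to likely under-counting and a missing comparison.

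A reader might infer more than the documents support:

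- **That the trial will under-count, or cannot attribute any symptom to the device.** A complaint that begins under supervision while the headset is worn can be attributed clinically. What is missing is a comparison of rates.
- **That eye strain is an expected risk, or that these symptoms are the only risks.** Background mentions it only in terms of "improving visual function and mobility, and reducing asthenopia in visually impaired individuals". Potential Risks also names confidentiality: "Another area where there may be an opportunity for potential risk is in protecting patient privacy".
- **That Special Precautions denies the named symptoms.** Its sentence concerns additional risk and can be read as risk beyond what was already disclosed. The wording is loose, and reconciling it is enough.
- **That lingering symptoms will flatter the device.** This requires the device to be tested first and symptoms to outlast the break. The documents establish neither.

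The reply does not remove the gap: no described procedure asks the question in either condition.

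**Conclusion.** The point holds in a limited form. The protocol names three physical device effects and describes no procedure or analysis that asks about them, so they are likely to be under-counted, and their rates with and without the device cannot be compared from the planned data. This conclusion comes from reading the procedures and does not depend on the illustrative figures.

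The size of the under-count is not known. The figures are correct arithmetic on assumed symptom and capture rates, and supervision could raise capture above the values assumed. Full capture does not rescue the pilot either: at a 20% true rate it would still record no case with probability 11% to 17%.

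The possible home use sharpens the point, since no symptom record is described for that period and the seated, supervised safeguards do not apply to it. This is a cheap improvement to the safety data; it does not invalidate the efficacy comparison.

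**What to change.** - **Study Procedures:** add a brief scripted checklist of disorientation, dizziness, blur and eye strain, asked by the tester already present, at baseline and at the end of each condition. Eye strain is included because Background calls it an open question. If a second visit takes place, the checklist should also cover the period of home self-training.
- **Recording:** note the condition and the test order with each checklist and each adverse event.
- **Statistical Analysis Plan:** report paired within-subject counts or changes with exact confidence intervals, as description and not as a formal test.
- **Reconcile:** bring the Special Precautions sentence, and the seated and supervised safeguards in Potential Risks, into line with the symptoms named there and the home use allowed in Study Procedures.

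The cost is a short amendment, one form and about a minute per time point: 3 × 1 = 3 minutes in a visit of about 120, with no added staff. Prompting will raise the reported symptom count. Because subjects know when they are wearing the device, the no-device ratings control for that only in part.

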**Evaluation of a Head Mounted Electronic Visual Enhancement Device
in Low Vision Patients**

NCT-03794752

10-10-2016

**The University of Texas Southwestern Medical Center at Dallas
Institutional Review Board**

PROJECT SUMMARY

Principal Investigator: [name], MD

Sub-Investigator: [name] , MD

Study Title: Evaluation of a Head Mounted Electronic Visual Enhancement Device in Low Vision Patients

Name and Address of Study Sponsor:

Evergaze Technology LLC

[name]

[name]

[contact]

[contact]

Purpose: To investigate the visual impact of a head-mounted electronic visual enhancement device in individuals with low-vision.

Background: Retinal Degeneration (RDEG) is a very prevalent blinding disease. An estimated 30% of the population older than 75 years of age has some degree of macular degeneration. About 12% of patients with RDEG end up having advanced disease. Several studies have shown that self-reported quality-of-life scores for patients with choroidal neovascularization (CNV) secondary to RDEG are worse than those reported by patients with AIDS (receiving treatment) and chronic obstructive pulmonary disease. Moreover, the levels of anxiety and depression were comparable. Despite recent advances in the treatment of choroidal neovascularization, every week we see patients that can attest to the fact that clinical outcomes remain suboptimal; patients that lose their ability to read, drive, or recognize the faces of their grandchildren and friends despite receiving the best

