This study will be a prospective, non-randomized study of low-vision individuals diagnosed with either retinal degeneration (RDEG) or diabetic macular edema with ETDRS visual acuity from 20/60 to 20/400 in both eyes from the University of Texas - Southwestern (UTSW) Medical Center at Dallas. Specifically, the primary objective of this testing is to establish the benefits of a wide field-of-view (FOV) monocular head-mounted visual enhancement device display (HMD), aiding the most degraded eye, as compared to best corrected visual acuity with glasses. It should be noted that in this approach, the HMD incorporates a camera, mounted coaxially with the visual axis of the eye with worse vision, and also image-enhancing or correction algorithms. Following review and execution of the informed consent, each subject will undergo an examination of their eyes, including: 1) ETDRS Best-corrected

distance visual acuity; 2) Best-corrected near visual acuity; 3) Tests based on questions 5, 6, 7 and 11 of the National Eye Institute 25-item visual function questionnaire (NEI VFQ-25).

- a. Question 5: Reading speed using a standard paragraph

English Paragraph Reference: 3-Minute Reading Assessments, Rasinski TV and Padak N, 2005. Scholastic Inc., NY

Spanish Paragraph Reference: Reference:
<http://www.cuadernosdigitalesvindel.com/libres/lenguaje.php>

Grade 5: Form A

| | |
|---|----|
| Last week, my family went to the county fair. My father is a volunteer firefighter, so he was working at the fair. My mom and sister and I went to meet him. I am very glad we did; it was a great night. When we arrived, the fair was very crowded and finding my dad was like finding a needle in a haystack. We finally found him because we heard the fire truck siren blaring and knew he would be there. Showing off the fire truck is my dad's favorite pastime; that truck is his pride and joy. | 11 |
| | 23 |
| | 37 |
| | 50 |
| | 62 |
| | 72 |
| | 82 |
| | 94 |
| | 98 |

Grade 5: Form C

| | |
|--|----|
| Lightning crashes, thunder booms, and the earth shakes with the power of the storm. This storm is holding us captive in the lobby of the grocery store. Looking out the huge glass windows, we see an angry sky. It seems to be daring us to come outside and make a mad dash for our car. | 8 |
| | 20 |
| | 31 |
| | 43 |
| | 55 |
| Through the pelting rain we see our brave little minivan. It is just waiting for us to fill its trunk with the week's food and its seats with our bodies. | 67 |
| | 81 |

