Periodically, the IRB will examine research studies conducted at UTSW Medical Center at Dallas. This audit process confirms whether a research project is being performed in an ethical manner, the protection of an individual who has given consent, and the researcher or his designee is following the regulatory codes of the university and government agencies such as FDA. All effort will be made to ensure patient confidentiality but there are times where the IRB representative will need to review the patient record to ensure that all elements of the study are being properly documented as specified in the protocol.

Potential Benefits:

The subjects may not receive direct medical benefit from taking part in the study. The knowledge gained from the study is to help define systems requirements for a device to assist low-vision persons with increased functionality. A \$100 stipend will be provided to patients to help offset any inconvenience from the 2 hours study visits.

Statistical Analysis Plan

A pilot study for this trial (8-10 subjects) will test the feasibility of improving sight for low-vision individuals. Statistical analysis will be performed on results based on the tests described in the protocol. Paired T-test analysis will be used to determine whether there are differences in vision and recognition when subjects are wearing or not wearing the sight enhancement device. Once the pilot study data shows that there may be differences vision using in relation to the testing parameters when

using the visual enhancement device, we will expand the study to a sample size of 20 individuals to collect data that will be sufficient to achieve appropriate statistical power and determine whether there is statistical significance between using vision using the enhanced vision device and vision without the device.

National Eye Institute
Visual Functioning Questionnaire - 25
(VFQ-25)

Version 2000

(INTERVIEWER ADMINISTERED FORMAT)

January 2000

RAND hereby grants permission to use the "National Eye Institute Visual Functioning Questionnaire 25 (VFQ-25) July 1996, in accordance with the following conditions which shall be assumed by all to have been agreed to as a consequence of accepting and using this document:

1. 1. Changes to the NEI VFQ-25 - July 1996 may be made without the written permission of RAND. However, all such changes shall be clearly identified as having been made by the recipient.

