| Stopped doing this because of your eyesight | 5 |
| Stopped doing this for other reasons or not interested in doing this | 6 |

7. Because of your eyesight, how much difficulty do you have finding
something on a crowded shelf?
(READ CATEGORIES AS NEEDED)

(Circle One)

No difficulty at all..... 1
A little difficulty..... 2
Moderate difficulty..... 3
Extreme difficulty..... 4
Stopped doing this because of your eyesight 5
Stopped doing this for other reasons or not
interested in doing this..... 6

11. Because of your eyesight, how much difficulty do you have seeing
how people react to things you say?
(READ CATEGORIES AS NEEDED)

(Circle One)

No difficulty at all..... 1 A
little difficulty..... 2
Moderate difficulty..... 3
Extreme difficulty..... 4
Stopped doing this because of your eyesight 5
Stopped doing this for other reasons or not
interested in doing this 6

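### The timed tasks have no time limit and no value for an unfinished task, so a subject who finishes in only one condition has no paired difference to test

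*Combined protocol and SAP*

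**What the plan says.** The Statistical Analysis Plan states that "Statistical analysis will be performed on results based on the tests described in the protocol" and names one method: "Paired T-test analysis will be used to determine whether there are differences in vision and recognition". It gives no scale, no alternative test and no rule for a missing value. It adds that the study will expand to a "sample size of 20 individuals to collect data that will be sufficient to achieve appropriate statistical power".

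The tasks are defined in the Concise Summary of Project, item 3:

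- Reading (3a): "Question 5: Reading speed using a standard paragraph".
- Shape board (3b): "measure the time it takes them to complete it".
- Shelf search (3c): "Repeat 3 times and record the time it takes the patient for each attempt".

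Each subject does these with and without the device, with a 20-minute break between (Study Procedures). No section gives a maximum time, a code for not finished, or a value to enter. The 2-hour figure under Potential Risks and Potential Benefits is the length of the visit. The three minutes in the title of the English reading source belong to a book title and set no limit.

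The documents themselves suggest that some subjects may not manage a task. The Background mentions "patients that lose their ability to read, drive, or recognize the faces of their grandchildren and friends", inclusion criterion 4 extends to 20/400 in the better eye, and the VFQ-25 items behind the tests offer the answer "Stopped doing this because of your eyesight". The performance tests have no matching outcome.

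**The concern.** A paired t-test needs two values per subject. Someone who completes the board with the device but not without it supplies one. Unless a value is assigned, that subject leaves the analysis, and the same holds for someone whom the device hinders. These are the subjects with the largest change in either direction. In a study of 20, after a pilot of 8-10, one or two of them matter.

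In practice a tester must stop a struggling subject at some point in a 2-hour visit. The plan does not fix that point or make it equal in the two conditions, and the tester can see whether the device is worn. A value chosen after testing would be chosen with the result in view.

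**Working it through.** **1. The plan's own figure.** The 20 subjects cannot be reproduced, because no alpha, power, effect or SD is stated. From the noncentral t distribution, 20 pairs give 80% power at two-sided 0.05 if the mean difference divided by its SD is about 0.66 (noncentrality 0.66 × √20 = 2.95, 19 df). With that effect, 18 pairs give 75% and 16 pairs 70%. This treats the lost pairs as typical. Subjects able in only one condition are not, hence the simulation below.

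**2. Inputs.** Only n = 20 comes from the documents. Assumed: log time = log(60 s) + subject effect (SD 0.9) + log(0.75) if the device is worn + error (SD 0.4 per measurement); one measurement per condition; two-sided 0.05.

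**3. Some subjects can do the task only with the device.** Power in %:

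| Able only with device | t-test on seconds, dropped | t-test on seconds, kept at 300 s | Signed-rank on log differences, kept at 300 s |
|---|---|---|---|
| 0 | 34 | 42 | 55 |
| 1 | 32 | 44 | 63 |
| 2 | 31 | 58 | 71 |
| 4 | 26 | 89 | 86 |

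The first row loses nobody, so its gaps (42 − 34 = 8 points; 55 − 34 = 21 points) come from capping, scale and choice of test. Subtracting them gives a rough measure of what keeping the subjects adds:

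- Same t-test: (44 − 32) − 8 = 4, (58 − 31) − 8 = 19 and (89 − 26) − 8 = 55 points for 1, 2 and 4 subjects.
- Signed-rank: (63 − 32) − 21 = 10, (71 − 31) − 21 = 19 and (86 − 26) − 21 = 39 points.

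With between-subject SD 0.5, the signed-rank gap is 56.0 − 46.7 = 9.3 points with nobody lost and 72.5 − 42.0 = 30.5 with two lost, a net 21.2.

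**4. Reverse case.** If two subjects fail only with the device and the other 18 follow ratio 0.75, the t-test without the two is significant in about 30% of trials, against about 10% for signed-rank with them kept at the limit. Dropping them hides the failures.

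**5. Slow subjects merely stopped at 120/180/300 s.** At ratio 0.60, complete pairs average 14.9/17.2/18.9. Pairs finished only with the device average 2.9/1.8/0.8, and only without it 0.3/0.2/0.1. The t-test on seconds in complete pairs has 75.8/81.6/82.8% power, against 75.6% if everyone finishes. At ratio 0.75 it has 32.1/37.5/39.1%, against 33.6%. The cut-off removes the longest and most variable times, so power hardly falls or even rises. The estimated ratio moves from 0.60 to 0.63/0.62/0.61.

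**6. Reading speed.** Same model, between-subject SD 0.3/0.5/0.7/1.0, two of 20 unable to read without the device. Dropping them gives the t-test 48/43/36/27% power. Entering 0 gives 68/63/54/41% with the t-test and 69/68/65/62% with signed-rank.

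**7. Validity and scale.** With no effect, the t-test on seconds rejects in 4.6/4.4/4.1/3.3% of trials over the same SDs. When times are skewed but the device saves a constant number of seconds with symmetric noise, the t-test on seconds keeps its 80% power, while the log t-test has 70-75%.

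**The case against.** The SAP nowhere says that incomplete pairs will be dropped. With no limit, slow subjects may simply finish, or staff may enter some value. The evidence that subjects will fail is indirect: the Background passage is general, the questionnaire answer concerns daily life, and no failure rate is given. All of this stands. Dropping is what the method does by default, and the plan sets nothing in its place.

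The named test also works once a value exists. On log times capped at 300 s, a paired t-test has 56/63/73/89% power for 0/1/2/4 such subjects, about the same as signed-rank. The missing value is therefore the main fault, and the choice of test is secondary.

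If failures are recorded, able and unable can still be compared by an exact McNemar test without any limit. That rescue is weak at this size: five discordant subjects all in one direction give p = 2 × 0.5^5 = 0.0625, and six give 0.031. A limit common to both conditions cannot be imposed after testing.

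The powers above are for one measurement per condition. Averaging three raw shelf times at ratio 0.75 gives 90% or 73% (between-subject SD 0.5 or 0.9) when everyone finishes, so the levels do not carry over to the shelf task.

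A reader might infer that a t-test loses power whenever times are skewed. It does so only if the paired differences are skewed, as with a proportional effect (step 7), and the documents give no data to show which applies.

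**Conclusion.** The omission is certain: three tasks are scored by time or speed, with no limit and no value for an unfinished task, and the one named test cannot use a subject measured in one condition only. Its size is not known. Under the assumed inputs, two subjects of 20 able only with the device are worth about 19 points of power, net of scale and capping. Two who fail only with it would leave the named test significant about three times as often as a test that counts them (30% against 10%). If subjects are only slow and are cut off, the loss of power is small or nil.

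Two stronger readings are not supported. The raw-seconds t-test is not invalid: its type I error stayed below 5%. Nor does the whole distance from 34% to 55% or more measure lost subjects, since 21 points of it are present when nobody is lost.

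The point does not undermine the design, but it should be settled before testing starts.

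**What to change.** Before the first subject, state in the protocol and SAP:

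1. One time limit per task, reading included, the same with and without the device.
2. An unfinished board or shelf attempt is entered at the limit. Reading is scored as words read within the limit per minute, and 0 if none.
3. One value per subject per condition (shelf: the average of the three attempts), tested with the exact Wilcoxon signed-rank test on paired differences. It depends less than the t-test on where the limit is set. Zero differences are removed and counted. The log scale is reasonable for times if a proportional effect is expected, but it is not required.
4. Finished and not finished are reported by condition for each task.

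The cost is a few sentences and a finished yes/no box on the data sheet. Eight board and shelf runs (one plus three, twice) at 120/180/300 s take at most 16/24/40 minutes. With one reading paragraph per condition, ten runs take at most 20/30/50. The visit leaves 120 − 20 = 100 minutes after the break, which must also hold acuity, video and questionnaire.

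There are downsides. Detail is lost at the limit, and ratios from capped times are pulled towards no effect (0.65/0.63/0.61 for a true 0.60 at the three limits) and should be labelled so. Signed-rank loses about 2 to 3 points of power against a log t-test when everyone finishes.
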